No physical specimens will be obtained. Data will be kept on encrypted laboratory computers, securely locked in the Woodruff Memorial Research Building and behind the Emory University 'Firewall' maintained by Information Technology Services. Data will consist of video-electrophysiological recordings and records from the testing session. Data will only be accessed and used by study staff. Study staff will de-identify the data by assigning each participant an alphanumeric ID (study number) as a reference. Any publication or presentation that uses the data from patients in this study is reported without identifying information. Data will be kept for at least six years after creation, thus the duration of the IRB and then for as long as required by any funding obtained for the project.

Sharing Results with Participants

This work (with no identifying information) will be shared with the epilepsy community and the work will result in peer-reviewed publication and presentations targeted to the epilepsy community. The epilepsy community consists not only of health care workers, but patients and their families, researchers, educators, administrators, public health and policy workers. Overall, we hope that the data obtained here will improve the care of patients treated with neuro-stimulation devices.

Study Timelines

Duration of individual patient involvement is 3-1-2 hour sessions over the course of 1 week. We estimate enrollment of patients to occur over the course of 1 year. The total study is anticipated to take place over the course of 2 years including data analysis.

Inclusion and Exclusion Criteria

Screening- Patients are known to the PIs in the context of their clinical work. In order to be eligible to participate in this study, an individual must meet all of the following criteria:

Inclusion criteria

- 1. Provision of signed and dated informed consent form
- 2. Male or female, aged 18-65
- 3. Diagnosed with lesional or non-lesional mesial temporal (hippocampal) seizure onset confirmed on SEEG monitoring
- 4. Implanted with depth electrodes for localization of seizure onset with multiple hippocampal electrode arrays

Exclusion criteria

- 1. Any patient who is unwilling or unable to provide consent
- 2. Women who are pregnant
- 3. Patients under 18 years
- 4. Incarcerated persons

Vulnerable Populations

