We are not studying a vulnerable group and will not include children, incarcerated persons, persons with cognitive disability or persons who are unable to give consent.

Local Number of Participants

Based on our power analysis, we estimate needing about 18 subjects for our analysis. Other studies in our Unit have typically had consent rates of 80% for eligible patients. We admit about 50 patients per year for intracranial EEG monitoring, with approximately 50% having mesial temporal lobe epilepsy.

Recruitment Methods

All patients entering our Intracranial Monitoring Unit who meet inclusion criteria will be approached for potential participation after recovery from the implantation surgery (>= 72 hours after implantation).

Patients with refractory suspected MTLE undergoing sEEG represent an accessible patient population from which participants may be recruited. As a high volume tertiary care epilepsy center (14 epileptologists, 3 nurse practitioners, and 2 epilepsy neurosurgeons), the Emory Epilepsy Center has unparalleled access to a large and continuously growing population of patients with refractory epilepsy. Emory is the only Level IV epilepsy center (including an active epilepsy surgery program) in the greater Atlanta area (a city of > 6 million people). Atlanta has one of the largest African American populations of any metropolitan area in the United States. 36% of the patients seen in the Emory Epilepsy Clinic are African American, and 56% of the patients seen are women.

Based on our past clinical volume, we estimate that >20 patients with MTLE will undergo SEEG per year. Study subjects will be recruited from this pool of patients. Our recruitment and retention rates for current and recent research protocols in SEEG patients have been ~80%. We are targeting to enroll 18 subjects, which should be feasible given our historic volume and recruitment rates.

Withdrawal of Participants

If the patient requests to withdraw from the study, all research and clinical records maintained outside the clinical record will be erased, with documentation of the original consent and that the subject has withdrawn from the study.

Risks to Participants

Referred Pain from Meningeal and Large Vessel Stimulation. This is unlikely to occur during hippocampal stimulation, but can be minimized and is not uncomfortable when stimulation intensity is increased gradually.

Seizure

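### About 18 subjects are needed for the analysis, but exactly 18 are enrolled at about 80% retention with no attrition allowance, so about 14 are expected to complete

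*Combined protocol and SAP*

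**What the plan says.** The number 18 has two roles in the protocol. Under Local Number of Participants it is the requirement for the analysis: "Based on our power analysis, we estimate needing about 18 subjects for our analysis". Under Recruitment Methods, and again under Resources Available, it is the enrolment target: "We are targeting to enroll 18 subjects, which should be feasible given our historic volume and recruitment rates". The Study Summary lists 18 as the sample size.

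In both places the sentence just before the target gives the expected rates: "Our recruitment and retention rates for current and recent research protocols in SEEG patients have been ~80" per cent. Consent has its own figure under Local Number of Participants: "Other studies in our Unit have typically had consent rates of 80% for eligible patients".

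Under Withdrawal of Participants, when a patient asks to withdraw, "all research and clinical records maintained outside the clinical record will be erased". The protocol contains no attrition allowance and no rule for replacing subjects.

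Study Endpoints names two analyses: a repeated-measures mixed model for the biomarkers, and a paired t-test of free recall with and without ADMES. The power analysis is mentioned but not shown: no alpha, power, effect size or standard deviation is given.

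On accrual, Study Timelines says "We estimate enrollment of patients to occur over the course of 1 year". Two yearly volumes are printed: "we estimate that >20 patients with MTLE will undergo SEEG per year", and "We admit about 50 patients per year for intracranial EEG monitoring, with approximately 50% having mesial temporal lobe epilepsy".

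**The concern.** A number required for the analysis equals the number to be enrolled only if nobody is expected to be lost. Here the protocol itself reports retention of about 80% and then sets the two numbers equal.

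Loss is plausible under this design. There are three sessions, the patient may stop at any time, and the safety rules end testing in some subjects. A patient who withdraws leaves no research data to analyse.

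The sentence about the power analysis is the protocol's only justification of its size. If the expected analysis set is smaller than that sentence requires, a reader would take the study to be sized as the power analysis asked when, on its own figures, it is not.

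**Working it through.** **Reproducing the 18.** This cannot be done, because no power inputs are printed. I take 18 at face value as the analysis requirement.

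**Inputs**
- Needed for analysis: about 18 (Local Number of Participants).
- Enrolled: 18 (Study Summary, Recruitment Methods, Resources Available).
- Retention: about 80%, reading the joint statement on recruitment and retention as about 80% for each (Recruitment Methods, Resources Available).
- Attrition allowance or replacement: none stated.

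**Step 1: expected completers = enrolled × retention**
- At 80%: 18 × 0.80 = 14.4, about 14. The shortfall is 18 − 14.4 = 3.6, or 3.6/18 = 20%.
- At 90%, as a sensitivity value: 18 × 0.90 = 16.2, about 16.

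**Step 2: chance of keeping all 18, if losses are independent**
- At 80%: 0.80^18 = 0.018, about 2%.
- At 90%: 0.90^18 = 0.150, about 15%.

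**Step 3: enrolment that would match the stated need**
- 18/0.80 = 22.5, so 23 subjects. This shows the size of the gap; it is not the change proposed.

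**Step 4: illustration of the power loss.** Assume a paired t-test at two-sided 5%, with standardised effect d, n − 1 degrees of freedom and noncentrality d√n. Choose d to give the assumed power at n = 18, then recompute at smaller n:

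| Assumed power at 18 | d (SD of the differences) | Power at 16 | Power at 14 |
|---|---|---|---|
| 80% | 0.70 | 75% | 68% |
| 90% | 0.81 | 86% | 80% |

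The effect detectable with 80% power thus rises from 0.70 SD at n = 18 to 0.81 SD at n = 14.

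**Step 5: accrual, for enrolment only, at 80% consent**
- 20 a year: 20 × 0.80 = 16 enrolled; 18/16 × 12 = 13.5 months to enrol 18.
- 23 a year: 23 × 0.80 = 18.4 enrolled.
- 25 a year (50 × 50%): 25 × 0.80 = 20 enrolled; 18/20 × 12 = 10.8 months to enrol 18.

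**The case against.** **The 80% may not apply here.** It is one approximate figure, given jointly for recruitment and retention, and it comes from other protocols. This study is three sessions within a week in patients who are already in hospital, so retention could be better. That stands as a caution about the exact number. It does not remove the gap: at 90% retention about 16 remain, and the protocol offers no other retention figure.

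**Completers are not the same as subjects analysed.** The erasure rule covers patients who ask to withdraw, not those whose testing is stopped. The mixed model can use partial data from subjects who stop early. This stands, so 14 should not be read as a firm count for the biomarker analysis. It is a fair expectation for the paired comparison, which needs both conditions from each subject.

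**The power figures are hypothetical.** This also stands. The paired test belongs to the secondary objective, and nothing says that 18 was derived from it. A reader might infer that the study's power has been shown to be overstated. The documents do not support that, because they state no power. Steps 1 to 3 do not depend on the illustration.

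**Accrual.** A reader might also infer that the clinic's volume cannot supply 18 subjects in the stated year. The documents do not support that either. The figure of more than 20 a year is a floor, 23 or more would be enough, and the other printed volume, about 25, enrols 20. The one-year estimate concerns enrolment, not retained subjects, and it sits inside a two-year study. At most, more than 20 a year does not by itself establish 18 enrolled in one year.

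**Conclusion.** The point holds for the analysis size. By the protocol's own figures, enrolling 18 is expected to give about 14 completers (14.4), a shortfall of 20% against the stated need of about 18. That is more than the word about can absorb.

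The conclusion rests on reading the joint 80% as the retention rate and on the absence of any attrition allowance or replacement rule. It applies most clearly to the paired memory comparison and less firmly to the mixed model. Its effect on power cannot be computed from the documents; under the assumed paired t-test, power falls by about 10 to 12 percentage points at n = 14.

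The feasibility statement about enrolling 18 is not shown to be wrong. For an exploratory study the point should be corrected, but it does not undermine the design.

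**What to change.** Keep enrolment at 18. In the Study Summary, Local Number of Participants, Recruitment Methods and Resources Available, state two numbers separately: 18 enrolled, and the number expected in the analysis, about 14 at the protocol's own 80% retention. If the sponsor expects better retention in this one-week inpatient study, state that rate with its reason and use the number that follows from it.

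Print the power inputs and say which analysis they belong to. Give the power or detectable effect at the expected number. For the mixed model, say whether subjects with partial sessions are included.

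Optionally, reconcile the two yearly volume figures in a sentence, since only the higher one by itself supports 18 enrolled in a year. The enrolment period need not change.

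The cost is wording only, with a somewhat less favourable power or detectable effect on record.

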Currently responsive neurostimulation (RNS, Neuropace, Inc) is the only FDA approved implantable neurostimulation device approved for neuromodulation directed at the hippocampus[3]. Recommended stimulation protocols include the use of high frequency (130-200 Hz) stimulation synchronized across implanted electrodes in response to detected seizures[5, 6]. In contrast, we have found that delivering asynchronous pulses distributed across a multi-electrode array of 16 micro-electrodes and stimulating at low (theta) frequencies is more effective than macrostimulation in controlling seizures in a rodent model of MTLE[7]. Asynchronous distributed multi-electrode stimulation (ADMES) can be delivered in a continuous fashion, but has the potential to be used in a responsive or optimized manner as well. These stimulation modes require the ability to identify biomarkers, or neurophysiologic features identifiable on recording on neural activity, indicative of impending seizures to optimize stimulation. The goal of the present study is to explore potential biomarkers that could distinguish between the interictal (between seizures), pre-ictal (before seizures) and ictal states (during seizures) to be used later for optimization of stimulation parameters in human subjects with implantable neurostimulation device.

As a high volume epilepsy surgery center, we have a unique opportunity to study electrophysiology directly from the brain in human subjects with epilepsy using electrodes already in place for clinical purposes. For many patients being considered for epilepsy surgery, invasive monitoring with stereo-EEG (SEEG) electrodes is needed to localize seizure onset zone. As part of routine clinical care, SEEG electrodes are used to monitor and record brain activity and for brain stimulation for the purpose of mapping brain function and eliciting seizures. During SEEG in patients with mesial temporal lobe epilepsy, depth electrode arrays are routinely placed in the hippocampus. We can utilize these implanted electrodes to both stimulate in an asynchronous manner and also simultaneously record local field potentials (LFPs) for analysis of biomarkers.

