LFPs will be continuously collected from intracranial depth electrodes before, during, and after stimulation using our data acquisition and stimulation system (Blackrock Microsystems, Salt Lake City, UT). The goal will be to measure the effect of different combinations of stimulation parameters (amplitude, frequency, and pulse width) on electrophysiological neural features (spectral power, synchrony) shown to correlate with the pre-ictal state. Multiple stimulation parameter sweeps will then be performed to identify parameters that modify these biomarkers most effectively. These parameter sweeps will initially focus on the range of stimulation parameters that will be feasible in a planned subsequent study using the RC+S device (Medtronic, MN) under a subsequent IRB to be submitted. However, given the greater flexibility of the externalized Blackrock CereStim device, additional stimulation patterns may be evaluated if supported by the initial results.

Connection of the stimulation and recording hardware (recording hardware takes a 'split' signal and also does not interrupt the clinical study) will be supervised and/or performed by a neurologist trained in electrophysiology, amplifiers and stimulators. Charge density is calculated based on the surface area of the electrode contacts, and will not exceed the 30 μ C/cm²/phase safety limit within the parameter space[8]. All stimulations will be composed of a biphasic charge-balanced square wave without an inter-phase delay. In all cases, iEEG will be continuously monitored by a neurologist during the session for the presence of after-discharges and seizures. Patients are admitted to the intracranial monitoring unit to have seizures, so this can coincidentally occur during the stimulation session.

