The proposed intracranial stimulation parameters are both historically common and proven safe in epileptic populations. Stimulation will be current-regulated and charge-balanced, with biphasic rectangular pulses. The anticipated electrode impedence is 1-4 k Ω . Stimulation will be bipolar, with the electrodes placed 1.5 mm apart (surface area, 0.059 cm). Prior to testing, current amplitude will be increased in a stepwise fashion in order to identify the threshold for afterdischarge (anticipated range 0.2-2 mA), and then decreased by 25% for the maximum amplitude for the duration of testing. The subjects will be blinded to stimulation condition. These parameters are similar to intracranial stimulation parameters used in other ongoing translational research protocols at Emory University Hospital over many years^{44,45}.

Pre-stimulation threshold testing:

Before the session, the epilepsy monitoring staff and patient will be consulted to determine if the patient has had any clinical seizures in the previous 2 hours. If the patient has had a clinical seizure in the previous 2 hours, then the experiment will be delayed until a 2 hour,

seizure-free period has been met. For each session, we will ask the patient for verbal consent to testing. During the entirety of all sessions, a study neurologist, clinical neurophysiologist, or neurosurgeon will monitor the subject and view the real-time EEG for afterdischarges. If any afterdischarges are observed, the protocol will be immediately halted and the patient assessed. Once afterdischarges have stopped, stimulation current will be decreased by 25-30% and testing will resume. If afterdischarges occur again, all testing will be aborted on the patient. If at any time clinical seizures are elicited during stimulation, all testing of that patient will be aborted.

The goal of the first session will be to establish the range of safe stimulation parameters that can be tested in subsequent parameter sweeps. The procedure for safety threshold testing is as follows:

- Seven stimulation frequency pulse-width combinations will be tested:
 - o 2 Hz, 450 μs
 - o 7 Hz, 450 μs
 - o 50 Hz, 450 us
 - o 90 Hz, 100 μs
 - o 90 Hz, 450 us
 - o 125 Hz, 100 μs
 - o 125 Hz, 450 us

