The stimulation parameters that we will use have been informed by our previous human studies our nonhuman primate data and fall within the range of typically used clinical stimulation parameters. When stimulation of the brain region within which seizures arise is performed, occasional epileptiform discharges can be seen. These are not seizures, but single events lasting < 200 ms that are the sign of increased excitability of the brain. These after-discharges can warn that seizure may occur with more intense stimulation. To avoid seizures, a neurologist will always be performing the stimulation and watching the real time EEG for these discharges. If a particular current intensity causes after-discharges, the current intensity of subsequent stimulations will be reduced.

Electrical stimulation of brain, using our technique and stimulus parameters, has minimal risk. The main risk is that stimulation might trigger a seizure, but this is uncommon given guidance by study staff who are neurologists trained in human electrophysiology and brain stimulation, and, with our stimulation parameters (careful attention to current density and emphasis of low-frequency stimulation; avoidance or appropriate decrease of current density and use of only low frequency stimulation in the hippocampal formation).

In the present study, current density will be kept below the typical safety limit of SEEG stimulation of 30 μ C/cm²/phase (thirty micro-Coulombs per square centimeter per phase), calculated based on current delivered per second and electrode surface area [8]. Stimulation will be graded, starting at very low current density then gradually increased.

During stimulation, the EEG will be observed by a trained neurologist physician with experience with reading intracranial EEG. If epileptiform discharges appear we will stop the stimulation run. If these continue we will use the ictal disrupt feature. We will then decrease the current and continue, but typically we will already have useful data at a lower current intensity. In the unlikely event that a seizure occurs, and becomes prolonged, lorazepam (1-2 mg IV) will be administered under the direction of a physician (there will always be a physician present), as per standard epilepsy monitoring unit protocol.

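### The risk section credits a low-frequency-only rule for the hippocampus that the stimulation design does not contain

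*Combined protocol and SAP*

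**What the plan says.** **The safety claim.** Under Risks to Participants, the General overview of stimulation safety considerations attributes the rarity of induced seizures partly to the study's stimulation parameters. A parenthesis then describes them. It first mentions "careful attention to current density and emphasis of low-frequency stimulation", a general tendency, and ends with the stricter "use of only low frequency stimulation in the hippocampal formation".

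**The vocabulary.** No section gives a numeric definition of low frequency. The Background offers two anchors: "stimulating at low (theta) frequencies is more effective than macrostimulation" for low, and "Recommended stimulation protocols include the use of high frequency (130-200 Hz) stimulation" for high.

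**The site.** The Background describes hippocampal depth arrays and continues "We can utilize these implanted electrodes to both stimulate in an asynchronous manner". The inclusion criteria require SEEG-confirmed hippocampal onset and more than one hippocampal array in every subject.

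**The frequencies.** Pre-stimulation threshold testing lists seven combinations from 2 to 125 Hz. Parameter search uses a 2-125 Hz grid. The ADMES section plans one 7 Hz and two 65 Hz patterns. ADMES effects on memory calls for the highest frequency the patient tolerates, without a number. The Intracranial stimulation protocol adds that "additional stimulation patterns may be evaluated if supported by the initial results".

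**The stopping rule.** Threshold testing allows one resumption at reduced current after afterdischarges, and then "If afterdischarges occur again, all testing will be aborted on the patient". The General overview says of epileptiform discharges during a run: "We will then decrease the current and continue".

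**The concern.** The Seizure subsection, just before the General overview, says where induced seizures have typically been seen at this centre: with high-frequency stimulation of the onset zone, or with repeated sequential pulses to a hippocampus from which seizures arise. By eligibility, every subject here has a hippocampal onset zone. A reader who then learns that the hippocampus receives low frequency only will conclude that the frequency part of this hazard has been designed out. If it has not, an IRB or DSMB member weighing the minimal-risk argument is relying on a mitigation that does not exist.

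The stopping-rule wording has a similar effect. Read alone, the General overview allows reduction and continuation without limit, whereas threshold testing stops at the second occurrence. Two versions of a patient-level stopping rule should not stand side by side.

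**Working it through.** There is no stated figure to reproduce. The check compares the clause with each section that sets stimulation.

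**1. Wide Bipolar (direct).** The Figure 3 legend gives two programs at a group frequency of 65 Hz and says the aim is tissue activated at 130 Hz at the seizure focus.
- Intended rate at the focus: 2 × 65 = 130 Hz.
- Focus location: hippocampal, by the inclusion criteria.
- Background range for high frequency: 130-200 Hz.

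So one planned pattern is meant to produce, in the hippocampal focus, a rate at the lower edge of the protocol's own high-frequency range. The legend describes Dual Ring Bipolar as the same apart from contact grouping. It may share this aim, but the aim is stated only for Wide Bipolar, so only that pattern is counted.

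**2. Threshold list (inferred site).** Frequencies: 2, 7, 50, 90, 90, 125, 125 Hz.
- At 50 Hz or more: 5 of 7.
- At 90 Hz or more: 4 of 7.
- At 130 Hz or more: 0 of 7.

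**3. Sweep grid (inferred site).** Number of frequencies: 125 − 2 + 1 = 124, matching the protocol.
- Above 7 Hz: 125 − 8 + 1 = 118, and 118/124 = 95.2%.
- At 50 Hz or more: 125 − 50 + 1 = 76, and 76/124 = 61.3%.
- At 130 Hz or more: 0.

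These count permitted grid values, not delivered stimulations. Only 180 patterns are drawn, sweeps begin from the range feasible on the later implantable device, and unsafe patterns are removed first.

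**4. Is there a restriction elsewhere?**
- The 125 Hz ceiling applies to the threshold list and sweep at any site.
- Threshold testing sets a current maximum for each frequency/pulse-width combination, at 80% of the current that caused side effects or unwanted LFP changes. This limits current, not frequency.
- Maximum pulse width depends on frequency. This limits pulse width.
- Patterns found unsafe or not possible on the hardware are dropped, whatever the region.
- The charge-density limit is 30 µC/cm² per phase. At the grid maximum, 3.5 mA × 450 µs = 1.575 µC, and 1.575 / 0.059 = 26.7 µC/cm², below 30. This assumes that the printed contact area of 0.059 is in cm². A per-phase limit does not vary with frequency, so it is not a hidden frequency cap. The General overview also speaks of current per second, but the unit it prints is per phase.

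None of these confines the hippocampus to low frequency.

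**5. Stopping rule.**

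| Occurrence | Pre-stimulation threshold testing | General overview |
|---|---|---|
| First | Halt, assess, cut current by 25-30%, resume | Stop the run, reduce current, continue |
| Second | Abort all testing in that patient | No separate rule |

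The two sections agree on the first occurrence and differ on the second.

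**The case against.** **Low might mean anything below 130 Hz.** The word is undefined, no programmed frequency reaches the Background's high range, and staying under that range could itself be called cautious. But the Background ties low to theta, not to everything under 130 Hz. If low did include 125 Hz, the clause would exclude nothing on the threshold list or grid. The intended effect of Wide Bipolar would still reach the high range.

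**The parenthesis is garbled.** It mentions avoidance before the low-frequency phrase and might be read as offering avoidance of the hippocampus as an alternative. The grammar is loose, but avoidance cannot be reconciled with a pattern aimed at a hippocampal focus, and the other branch still says only low frequency.

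**Some support is indirect.** This stands. Contacts for the threshold tests and sweep are not listed, so hippocampal delivery there is inferred from the Background and eligibility. The highest tolerable frequency in the memory trials carries no number and cannot show high-frequency use by itself. The grid percentages are not exposure.

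**There are limits on frequency.** This also stands: the 125 Hz ceiling and the removal of unsafe patterns apply to the hippocampus as to any site. The defect is the absence of a hippocampus-specific or low-frequency restriction, not of any limit.

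**The consequence is small.** Largely fair. The planned numeric frequencies are printed, the Seizure subsection names the hazard openly, and staff have a list to follow.

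**Conclusion.** The clause is wrong as written: it states a safety property that the design lacks, on a hazard the protocol itself names. The contradiction is direct for one of the three ADMES patterns and a strong inference for the threshold tests and sweep. It rests on two readings: that the seizure focus in the Figure 3 legend is the hippocampal onset zone required for eligibility, and that low does not stretch to 130 Hz.

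A reader might go further and infer that the trial is unsafe, that the minimal-risk argument fails, or that hippocampal frequency must be capped. The documents support none of these. A charge-density limit, graded current, per-combination current caps, live EEG review and abort rules all apply, and nothing here shows them to be inadequate. Nor do the documents show what participants were told, since the consent pages are not available. The point should be fixed, as a correction to a risk statement that reviewers rely on.

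The mismatch over a second afterdischarge is separate from frequency, but it sits in the same subsection, bears on patient safety and should be corrected with it.

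**What to change.** In the General overview of stimulation safety considerations:

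1. Delete the low-frequency-only clause.
2. State that the seizure-onset hippocampus may be stimulated at the planned frequencies: up to 125 Hz in threshold tests and sweep; 7 or 65 Hz programmed for ADMES, with about 130 Hz intended at the focus under Wide Bipolar.
3. Rest the seizure-risk justification on the safeguards that apply: the 30 µC/cm² per phase limit, stepwise current increase, the current cap for each frequency/pulse-width combination, continuous EEG review by a physician, and the abort rules for afterdischarges and clinical seizures.
4. Replace the reduce-and-continue sentence with the threshold-testing rule: reduce current and resume after a first occurrence of afterdischarges, and abort all testing in that patient after a second.

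The cost is a wording amendment and a slightly less favourable risk statement. Endpoints, analyses and stimulation settings stay as they are. A numeric frequency cap for hippocampal contacts is not required. It would be the alternative only if the investigators do intend such a restriction, and it would shrink the threshold list, the sweep grid and possibly the 65 Hz patterns.
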